Principal Investigator
[name] [name] MD
[name] FACS FRCS (c) FRCSI (Hon) FRCSE (Hon)

Head of Thoracic Surgery and Thoracic Oncology
Director Digestive Disease Institute Esophageal Center of Excellence
President Ryan Hill Research Foundation
Virginia Mason Medical Center
[name]
[name]
[contact]

Study Title:
**Influence of NSarcoPenia on Esophageal
Cancer ouTcomes (INSPECT study)**

APPROVED
12/10/2019
BRI IRB

Table of Contents

A. SPECIFIC AIMS.....	3
B. BACKGROUND AND SIGNIFICANCE	5
C. PRELIMINARY STUDIES	7
D. RESEARCH DESIGN AND METHODS.....	9
E. PROTECTION OF HUMAN SUBJECTS	13
F. REFERENCES	22
G. CONSULTANTS	24
H. APPENDIX.....	25

A. SPECIFIC AIMS

Hypothesis: Esophageal cancer is associated with changes in patient's body composition that are correlated with biochemical markers of cell metabolism (acetone) and systemic inflammation. Knowledge of these changes can influence patients' care through modification of treatments and outcome prediction.

Purpose: An observational, pilot study to assess longitudinal variation in exhaled acetone, body composition and other markers of nutritional status and inflammation in patients undergoing multimodal therapy for esophageal cancer. Where possible variations in these markers will be correlated with changes to early and late treatment outcomes as well as nutritional interventions that form part of patients routine care.

B. STUDY OUTCOMES

Primary outcome

- i. Longitudinal assessment of breath acetone in patients undergoing multimodal therapy for esophageal cancer

Secondary outcomes

- i. Correlation of breath acetone with alternate measures of nutritional status including anthropometric measurements, body composition, resting energy expenditure and blood parameters
- ii. Correlation of breath acetone and alternate measures of nutritional status with patient reported nutritional intake and quality of life
- iii. Assessment of the repeatability and accuracy of point of care testing of breath acetone using the Ketonix device

C. BACKGROUND AND SIGNIFICANCE

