Sample size: 35 patients (15 from St Mary's Hospital Imperial College Healthcare NHS Trust, London, UK recruitment center and 20 from Virginia Mason Medical center, Seattle, USA). Sample size has been determined pragmatically based on the predicted number of patients undergoing treatment for esophageal cancer in recruitment centers during the study period. It is noted that even in high volume centers such as Virginia Mason Medical Center and St Mary's Hospital the longitudinal accrual of patients at the time of diagnosis and definitive surgery seldom exceeds 20-30 patients per year. Accordingly number of patients decided from each site during the intended 8 month study period is a conservative estimate of study recruitment. It is intended that data obtained from this pilot study will support formal power calculations for future studies.

Aspects of recruitment, consenting, data collection, and data storage will be the responsibility of each of the recruiting center. Separate ethical approval for this study will be sought at both Virginia Mason Medical Center and St Mary's Hospital where the conduct of the research will be required to meet local standards. Responsibility for the conduct of research at each site will be assigned to the local lead ([name] at Virginia Mason Medical Center and Professor [name] at St Mary's Hospital).

Inclusion criteria:

Patients with the following characteristics will be eligible for inclusion in this study:

- i. aged 18-90 years
- ii. newly diagnosed (prior to treatment) with esophageal and/or gastroesophageal junctional cancer (adeno- or squamous cell carcinoma)
- iii. planning to undergo curative treatment, including surgical resection with neoadjuvant therapy

Exclusion criteria:

Patients with the following characteristics will not be eligible for inclusion in this study:

- i. pregnant females
- ii. without malignant esophageal disease
- iii. inability or unwillingness to provided informed written consent

Methodology: patients undergoing curative treatment for esophageal cancer will be recruited at the time of routine clinical assessment shortly following initial diagnosis

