and will undergo clinical evaluation at two study time points: (1) staging investigation (e.g. laparoscopy or endoscopy) and (2) definitive surgical resection. Study time points have been judiciously chosen to coincide with interventions that form part of patient's routine clinical care. It is intended that sampling will occur on the day of each intervention/surgery following a routine period of fasting.

Breath sample collection:

Analysis of breath acetone from samples collected from Virginia Mason Medical Center and St Mary's Hospital will be performed using a KETONIX® point of care device. Patients will be asked to exhale directly into this handheld device, which provides an on-line and real-time measurement of breath acetone concentration in parts per million.

At St Mary's Hospital breath acetone analysis will also be performed using the Proton Transfer Reaction Mass Spectrometry (PTR-MS) in order to provide cross platform validation of results.

Blood sampling:

At each study time point a single sample of venous blood (15ml) will be collected for the purpose of determining serum concentrations of a number of metabolic and inflammatory markers, e.g. C-reactive protein (CRP), albumin, lipid profile, glucose, insulin, acetone, insulin-like growth factor (IGF), macrophage inhibitory cytokine-1 (MIC-1), interleukin-1 (IL-1), interleukin-6 (IL-6), interleukin-10 (IL-10), and; tumor necrosis factor alpha (TNFa). Once collected, samples will be centrifuged and the supernatant (serum) will be aliquoted for storage at -80°C.

Analysis of serum CRP, albumin, lipid profile, glucose and insulin will be performed within the biochemical pathology laboratories of the individual recruitment centers. The remaining biochemical parameters will be analyzed using commercial available enzyme-linked immunosorbent assays (ELISA) kits. An agreement has been reached with the Benaroya Research Institute at Virginia Mason to conduct the ELISA analysis for all samples.

Indirect calorimetry:

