Univariable and linear regression analysis will be used to compare exhaled acetone concentrations with body composition parameters. The coefficient of variation will be determined for repeated measurements recorded using the Ketonix device. Acetone concentrations measures using the Ketonix device and PTR-MS (St Mary's Hospital only) will be compared using Bland Altman plots. Comparisons between continuous data will be made using either the Mann-Whitney U test or Student t test, whilst categorical variables will be compared by χ^2 or Fischer exact test. Statistical significance will be assigned to 2-sided P values <0.05 .

F. PROTECTION OF HUMAN SUBJECTS

Risks to human subjects:

Human Subject involvement and characteristics

Human subjects will be enrolled into this study. The purpose of recruiting human subjects is to determine the influence of esophageal cancer and neoadjuvant therapy on nutritional status and inflammatory markers. Recruitment of human subjects is critical to achieving the intended outcomes of this study.

Patients with newly diagnosed esophageal and/or gastroesophageal junctional cancer (adeno- or squamous cell carcinoma will be recruited from Virginia Mason Medical Center (n=20) and St Mary's Hospital (n=15). Patients will be asked to donate an exhaled breath sample and blood sample (15ml) at two study time points. Patients' resting energy expenditure will also be determined and patients will be asked to complete a three day dietary diary, PG-SGA food intake and quality of life questionnaires at each study time point. Any other data that are utilised as part of this study originates from patients' routine clinical care and EMR.

We do not plan to enroll vulnerable subject groups (children, persons with mental disability, prisoners) where ability to give voluntary informed consent maybe questioned or compromised.

Enrollment:

Collaborating sites:

This work will be conducted as part of a collaboration between Virginia Mason Medical Centre (Seattle, USA) and St Mary's Hospital (Imperial College Healthcare NHS Trust, London, UK).

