APPENDIX III

Influence of pre-operative low carbohydrate diet and bariatric surgery on exhaled acetone levels:

Methodology: Patients at different stages of treatment for obesity were recruited to this single center cross-sectional study. Sample time points were: (i) at the time of initial attendance prior to dietary or surgical interventions; (ii) on the day of surgery following low carbohydrate diet, and; (iii) >3 months after either Roux-en Y gastric bypass or sleeve gastrectomy. The concentration of acetone within breath samples, collected into steel bags, was analyzed by selected ion flow tube mass spectrometry (SIFT-MS). Exhaled acetone was correlated with measures of weight loss and biochemical markers of nutrition.

Summary of key findings relevant to current application: Exhaled acetone was observed to vary significantly in patients receiving treatment for obesity. Higher levels of acetone were observed in patients following pre-operative diet and bariatric surgery: pre-diet 410 ppb (IQR 161-796); post-diet 1396 ppb (357-2990), and; postoperative 1693 ppb (1149-2547)($P < 0.0001$)(Figure IIIA).

[figure not shown]

Figure IIIA. Variation in exhaled acetone concentration
(Kruskal Wallis test, $P < 0.001$)

Exhaled acetone levels were inversely correlated to patient BMI ($\rho -0.262$, $P=0.005$), excess body weight (EBW, $\rho -0.264$, $P=0.005$) and percentage loss of EBW (for post-diet and postoperative patients; $\rho -0.375$, $P < 0.0001$) determined at the time of sampling. Exhaled acetone did not however correlate with rate of weight change after either dietary modification or surgical intervention ($P > 0.05$).

For EBW, the results of multivariate linear regression demonstrated that neutrophil count, glucose, acetone, and low-density lipoprotein concentration explained a significant amount of variation in patients BMI ($F(df\ 3,\ 43) = 7.4$, $P = 0.0001$, $R^2 = 0.41$, R^2 adjusted = 0.36). With the exception of glucose (Beta = 0.24, $t(46) = 2.00$, $P = 0.053$) each of these variables significantly predicted EBW within the model: neutrophil count (Beta = 0.41, $t(46) = 3.39$, $P = 0.002$), acetone (Beta = -0.34, $t(46) = -2.78$, $P = 0.008$), and low-density lipoprotein (Beta = -0.30, $t(46) = 2.42$, $P = 0.020$).

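### The primary outcome is change in breath acetone within the same patients, but the only general rule for continuous data offers Mann-Whitney U or a t test not stated to be paired

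*Protocol*

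**What the plan says.** Section B of the protocol gives a single primary outcome: "Longitudinal assessment of breath acetone in patients undergoing multimodal therapy for esophageal cancer". The purpose in section A is to "assess longitudinal variation in exhaled acetone, body composition and other markers of nutritional status and inflammation". Under Methodology in section E, patients "will undergo clinical evaluation at two study time points", namely the staging investigation and the definitive resection. Breath and blood are taken from the same patients on both occasions.

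There is no untreated group. Inclusion criterion iii requires patients to be "planning to undergo curative treatment, including surgical resection with neoadjuvant therapy". Section F says that patients are recruited to "determine the influence of esophageal cancer and neoadjuvant therapy on nutritional status and inflammatory markers".

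The Data analysis paragraph in section E names these methods:
- regression of exhaled acetone on body composition;
- a coefficient of variation ("The coefficient of variation will be determined for repeated measurements recorded using the Ketonix device");
- Bland-Altman plots for Ketonix against PTR-MS;
- for continuous data in general, "Comparisons between continuous data will be made using either the Mann-Whitney U test or Student t test";
- chi-square or Fisher's exact test for categorical data.

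Significance is set at two-sided 0.05. The paragraph mentions no paired t test, signed-rank test, mixed model or change score, and it ties no method to the primary outcome.

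**The concern.** With one cohort, two visits and neoadjuvant therapy planned for everyone, anything the study can say about change over treatment has to come from comparing each patient at surgery with the same patient at staging. Those observations are paired.

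The one rule broad enough to cover that comparison offers two tests. Mann-Whitney U cannot be paired. The Student t test is correct here only if run paired, which the text does not say. The rank option is also the more likely choice: in Appendix III the group reported its own acetone data as medians with wide interquartile ranges and analysed them with a Kruskal-Wallis test. That suited the earlier design, because "Patients at different stages of treatment for obesity were recruited to this single center cross-sectional study". It does not suit this one.

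At stake are the error rate and precision of the visit comparison for the primary outcome, in at most 35 pairs. The variance of within-patient change would also be the natural input to the later power calculations that the Sample size paragraph says this pilot will support.

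**Working it through.** **The plan's own figure.** 15 patients in London + 20 in Seattle = 35, as stated. The protocol gives no power, effect size or SD, so there is no calculation to reproduce and no stated figure is in dispute.

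**Inputs.** n = 35 and two-sided 0.05 come from section E. Three things are assumed: the between-visit correlation rho (0, 0.3, 0.5, 0.7), a true shift of 0.5 SD, and complete pairs with equal SD at both visits.

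**Standard error.** The mean change has variance 2·SD²·(1 − rho)/n. An unpaired test uses 2·SD²/n. For positive rho the unpaired standard error is therefore too large by a factor of 1/√(1 − rho). At rho 0.5 that is 1/√0.5 = 1.41.

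**Confidence interval half-width, in SD units.**
- Unpaired: t(0.975, 68)·√(2/35) = 0.477.
- Paired: t(0.975, 34)·√(2(1 − rho)/35) = 0.486, 0.406, 0.344 and 0.266 at rho 0, 0.3, 0.5 and 0.7.

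**Level and power.** These come from 200,000 simulated bivariate normal data sets per setting. The level is for no change and the power is for the 0.5 SD shift.

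| rho | True level, unpaired t / Mann-Whitney | Power, unpaired t / Mann-Whitney | Power, paired t / signed-rank |
|---|---|---|---|
| 0 | 5.0% / 5.0% | 54.1% / 51.8% | 52.9% / 50.3% |
| 0.3 | 2.0% / 2.1% | 54.9% / 52.3% | 68.0% / 65.4% |
| 0.5 | 0.65% / 0.73% | 55.5% / 52.6% | 81.9% / 79.6% |
| 0.7 | 0.05% / 0.09% | 57.5% / 54.3% | 96.0% / 95.0% |

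The noncentral t distribution gives paired t power of 52.9%, 68.0%, 82.0% and 96.0%, which agrees. A separate simulation with 20,000 data sets per setting (4,000 for the signed-rank test) gave the same picture. It also showed that with an assumed 28 complete pairs at rho 0.5, power is about 40% for Mann-Whitney against 72% for the paired t test and 70% for the signed-rank test.

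**Skewed data, illustration only.** The pre-diet interquartile range in Appendix III, 161 to 796 ppb, implies a log SD of ln(796/161)/1.349 = 1.18 if the data are lognormal. In 100,000 simulated lognormal data sets per setting with a shift of 0.5 log SD, power was as follows.

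| rho | Mann-Whitney | Signed-rank, raw scale | Paired t, log scale |
|---|---|---|---|
| 0 | 52% | 45% | 53% |
| 0.5 | 53% | 71% | 82% |

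At rho 0.5 the confidence limits lie a factor of exp(0.477 × 1.18) = 1.76 either side of the estimate unpaired, and exp(0.344 × 1.18) = 1.50 paired. Across the three interquartile ranges in Appendix III (log SD 0.59 to 1.58), the factors run from 1.33 unpaired against 1.22 paired to 2.12 against 1.72.

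**The case against.** The strongest reply is that the sentence never mentions visits. It sits beside chi-square and Fisher's exact tests, which are also for independent groups, and can be read as a between-group rule. Such contrasts exist here: sarcopenic or not, viscerally obese or not, with or without complications. On that reading the protocol merely leaves the visit test to a SAP, which is normal. This reading is possible, and silence alone would not be a finding. But the sentence has no such limit, the primary outcome is itself continuous, and the rule applied as written offers the visit contrast a rank test that does not fit it.

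Other points have weight:
- A Student t test can be paired. That is true, so only the rank option is wrong in every case.
- This is an observational pilot with no stated hypothesis on acetone change, and the section F sentence on neoadjuvant therapy names nutritional and inflammatory markers, not breath acetone. Both points are correct and lower the stakes. However, the paragraph sets a significance threshold, so testing is planned.
- The correlation is unknown and could be low, since treatment falls between the visits. At rho 0.1 the power is 54% unpaired and 57% paired; at rho 0.2 it is 55% and 62%.
- The Appendix III data come from obese patients in a cross-sectional study using a different instrument. The lognormal form also fits the post-diet row poorly: √(357 × 2990) = 1033 ppb against a reported median of 1396 ppb. The skewed-data figures, above all the top of the range, are therefore illustrative only.

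**Conclusion.** The concern holds. The protocol's only general rule for continuous data does not fit its only primary outcome, or at best leaves that outcome without a named method.

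The size depends on a correlation that the protocol does not give. There is no loss at rho 0 and a growing loss as rho rises. The direction is conservative for any positive correlation, so the rule adds no false positives there; the cost is missed change and wider intervals.

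The harm is modest. No stated figure is wrong and the data can be reanalysed. The SD of within-patient change can be computed whichever test is used, so the aim of informing later studies is not lost. The point still deserves correction because it touches the primary outcome and costs almost nothing to put right.

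**What to change.** In the Data analysis paragraph of section E, split the general sentence in two, along these lines:

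*Comparisons between time point 1 and time point 2 will use a paired t test (on the log scale if the data are skewed) or the Wilcoxon signed-rank test, and the mean within-patient change will be reported with its 95% confidence interval and SD. The Mann-Whitney U test and the two-sample t test will be used for between-group comparisons only.*

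A mixed model with a random patient effect is an acceptable alternative but is not needed. Reporting the SD of change gives the later power calculations the quantity they need. The cost is one or two sentences, with no new data and no new patients.

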APPENDIX I

Results of meta-analysis:

[figure not shown]

Figure IA. Summary meta-analysis of studies reporting the effect of sarcopenia on the survival of patients undergoing esophagectomy for esophageal cancer (HR 1.70, 95% CI 1.33 to 2.17, $P<0.0001$)

[figure not shown]

Figure IB. Summary meta-analysis of studies reporting the effect of sarcopenia on the occurrence of postoperative respiratory complications in patients undergoing esophagectomy for esophageal cancer (OR 2.03, 95% CI 1.32 to 3.11, P=0.001)

[figure not shown]

Figure IC. Reported incidence of sarcopenia in esophageal cancer patients determined prior to esophagectomy

A draft of the manuscript of this meta-analysis is available from [name] upon request

[contact]

APPENDIX II

Synthetic pathway of endogenous acetone synthesis:

[figure not shown]

Figure IIA. Synthetic pathway of endogenous acetone synthesis

APPENDIX III

Influence of pre-operative low carbohydrate diet and bariatric surgery on exhaled acetone levels:

Methodology: Patients at different stages of treatment for obesity were recruited to this single center cross-sectional study. Sample time points were: (i) at the time of initial attendance prior to dietary or surgical interventions; (ii) on the day of surgery following low carbohydrate diet, and; (iii) >3 months after either Roux-en Y gastric bypass or sleeve gastrectomy. The concentration of acetone within breath samples, collected into steel bags, was analyzed by selected ion flow tube mass spectrometry (SIFT-MS). Exhaled acetone was correlated with measures of weight loss and biochemical markers of nutrition.

Summary of key findings relevant to current application: Exhaled acetone was observed to vary significantly in patients receiving treatment for obesity. Higher levels of acetone were observed in patients following pre-operative diet and bariatric surgery: pre-diet 410 ppb (IQR 161-796); post-diet 1396 ppb (357-2990), and; postoperative 1693 ppb (1149-2547)($P < 0.0001$)(Figure IIIA).

[figure not shown]

Figure IIIA. Variation in exhaled acetone concentration
(Kruskal Wallis test, $P < 0.001$)

Exhaled acetone levels were inversely correlated to patient BMI ($\rho -0.262$, $P=0.005$), excess body weight (EBW, $\rho -0.264$, $P=0.005$) and percentage loss of EBW (for post-diet and postoperative patients; $\rho -0.375$, $P < 0.0001$) determined at the time of sampling. Exhaled acetone did not however correlate with rate of weight change after either dietary modification or surgical intervention ($P > 0.05$).

For EBW, the results of multivariate linear regression demonstrated that neutrophil count, glucose, acetone, and low-density lipoprotein concentration explained a significant amount of variation in patients BMI ($F(df\ 3,\ 43) = 7.4$, $P = 0.0001$, $R^2 = 0.41$, R^2 adjusted = 0.36). With the exception of glucose (Beta = 0.24, $t(46) = 2.00$, $P = 0.053$) each of these variables significantly predicted EBW within the model: neutrophil count (Beta = 0.41, $t(46) = 3.39$, $P = 0.002$), acetone (Beta = -0.34, $t(46) = -2.78$, $P = 0.008$), and low-density lipoprotein (Beta = -0.30, $t(46) = 2.42$, $P = 0.020$).

APPENDIX IV

Methodology for calculating specific parameters of body composition:

CT or positron emission tomography with computed tomography scan acquired as part of patient's routine care will be acquired. Images at the anatomical level of L3 or the L3-L4 intervertebral disc space will be obtained and exported to a Digital Imaging and Communications in Medicine (DICOM) format. Images will be subject to automatic segmentation to determine cross sectional muscle and adipose area. Definitions of skeletal muscle index, sarcopenia and visceral obesity are provided below (15, 16).

Figure IVA. Example of automatic skeletal muscle (central panel) and adipose tissue (right panel) segmentation

Skeletal muscle index (SMI) will be calculated as the ratio of lean tissue area to height:

$$SMI \text{ (cm}^2/\text{m}^2\text{)} = \frac{\text{Lean tissue area (cm}^2\text{)}}{\text{Height (cm}^2\text{)}}$$

Sarcopenia will initially be defined as SMI <52.4 cm²/m² for men and <38.5 cm²/m² for women (15). The following formulae will be used to determine lean body mass and fat mass:

$$\text{Lean body mass (Kg)} = 0.30 \times [\text{Lean tissue area (cm}^2\text{)}] + 6.06$$

$$\text{Fat mass (Kg)} = 0.042 \times [\text{Total fat area (cm}^2\text{)}] + 11.2$$

Visceral obesity is defined as a fat area >163.8 cm² for men and >80.1 cm² for women.
